10.2. Disease Control Rate

The DCR is the proportion of subjects who have a CR, PR, or stable disease at 12 weeks following the start of Ad-RTS-hIL-12 immunotherapy using RECIST v1.1.

The DCR will be summarized by HER2 status group and overall. An exact 2-sided 95% confidence interval will also be presented.

For this calculation, responders are defined as those experiencing a CR, PR, or stable disease. Non-responders are defined as those with PD. Those subjects that cannot be assessed will be treated as non-responders for the purposes of deriving the percentage of responders and confidence intervals.

10.3. Tumor response rate by irRC

The tumor response by irRC is based on the sum of the 2 largest perpendicular diameters (SPD) of all index lesions at baseline to provide the total tumor burden. At each subsequent tumor assessment, the SPD of the index lesions and of new, measurable lesions ($\geq 5 \times 5$ mm; up to 5 new lesions per organ: 5 new cutaneous lesions and 10 visceral lesions) are added together to provide the total tumor burden. The overall response according to the irRC is derived from time-point response assessments (based on tumor burden) as follows:

- irCR: complete disappearance of all lesions (whether measurable or not, and no new lesions) confirmation by a repeat, consecutive assessment no less than 4 weeks from the date first documented
- irPR: decrease in tumor burden $\geq 50\%$ relative to baseline confirmed by a consecutive assessment at least 4 weeks after first documentation
- irSD: not meeting criteria for irCR or irPR, in absence of irPD
- irPD: increase in tumor burden $\geq 25\%$ relative to nadir (minimum recorded tumor burden) confirmation by a repeat, consecutive assessment no less than 4 weeks from the date first documented

irORR and irDCR by irRC will be analyzed the same way as described above for tumor response using RECIST v1.1.

10.4. Progression-Free Survival (PFS) at Week 12

This is defined as the proportion of subjects who have 12-week progression-free survival after the start of Ad-RTS-hIL-12 immunotherapy. The PFS rate at Week 12 will be summarized by HER2 status group and overall.

An exact 2-sided 95% confidence interval will also be presented by HER2 status and overall.

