Complete Response (CR)	CR is declared if all of the following are true for target lesions: 
• The disappearance of all non-nodal target lesions• Any pathological lymph nodes must have a reduction in short axis to <10 mm.
Partial Response (PR)	PR is declared if there is a decrease of at least 30% in the sum of diameters of target lesions taking as reference the baseline sum of diameters of target lesions.
Progressive Disease (PD)	PD is only declared if all of the following are true for target lesions: 
• SOD of all target lesions increases at least 20% taking as reference the smallest SOD recorded at or after baseline• Actual SOD increase is ≥ 5 mm from the smallest SOD recorded at or after baseline
Stable Disease (SD)	SD is declared if target lesion assessment does not meet criteria for PR, PD or CR

Selection and Assessment of Non-Target Lesions:

Non-target lesions are all other lesions, including additional potentially measurable lesions and truly non-measurable lesions, such as lesions that are/will be injected with INXN-2001 and/or biopsied, all bone lesions, ascites, pleural and pericardial effusion, inflammatory breast disease, lymphangitic involvement of skin or lung, and brain lesions. Non-target lesions will be assessed qualitatively, and the possible assessments are CR, Non-CR/Non-PD (NN), and PD.

If pleural effusions or ascites (selected as non-target lesions at baseline) are stable in size or minimally enlarging, they will be assessed as NN. New fluid collections or any effusion that significantly worsens will be considered a sign of PD unless cytopathology results are available that support a non-malignant nature.

Non-target lesions should only be assessed as PD if the progression is unequivocal. In the setting of a subject who also has measurable disease, there must be an overall level of substantial worsening in the context of the overall disease burden. A modest increase in size of one or more non-target lesions is not considered sufficient to qualify for unequivocal progression status. In the absence of measurable disease, the change in the overall non-measurable disease burden should be comparable to at least a 20% increase in overall diameter or 73% in approximate overall volume.

New Lesions:

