Section in Amended Protocol	Revised Text/Section	Rationale for Change																													
	
assessments may occur at the discretion of the Investigator.
 
NOTE: In addition to the standard RECIST v1.1 guidelines established to evaluate antitumor responses to chemotherapeutic agents, antitumor response will be assessed using total tumor burden (TTB), where the sum of the products of the two longest diameters (SLD) is used to calculate Total Tumor Burden = SLD_{index lesions} + SLD_{new, for measurable lesions}. (Appendix 4)
 
17. Biopsies (PBx, FNA) will be collected for all subjects according to the table below, and were removed for Cycle 6 Day 7 and Follow-up Tumor Assessment.
 
  
 Activity	Screening Day -28 to -1	Cycles 1 and 3 ONLY	Post-Treatment Safety Assessment Visit	
 
 Pre-Registration	Post-Registration	Cycle 1 Day 7±1	Cycle 3 Day 7±1	28±3 days post-INXN-1001 dose	
   
 Biopsy / FNA^a		X^a	X^b	X^b	X	
 
 Tumor injected with INXN-2001			PBx^b	FNA^b	PBx	
 
 Non-Injected Tumor and/or Draining Lymph Node		PBx^a	PBx^b	FNA^b	PBx	
  
 
PBx: Punch biopsy (≥ 4 mm in diameter); FNA: fine needle aspiration biopsy
 
^a At screening, the PBx and FNAs should be obtained only AFTER subject registration/randomization has been completed (ie, after approval by sponsor for study participation) and before start of treatment.
 
^b PBx's and FNAs on Day 7 should be obtained after the Day 7 administration of INXN-1001 for subjects in Arms A and C. Note: NO PBx will be collected on Cycle 1
	Activity	Screening Day -28 to -1		Cycles 1 and 3 ONLY		Post-Treatment Safety Assessment Visit	Pre-Registration	Post-Registration	Cycle 1 Day 7±1	Cycle 3 Day 7±1	28±3 days post-INXN-1001 dose	Biopsy / FNA ^a		X ^a	X ^b	X ^b	X	Tumor injected with INXN-2001			PBx ^b	FNA ^b	PBx	Non-Injected Tumor and/or Draining Lymph Node		PBx ^a	PBx ^b	FNA ^b	PBx	
Revise biopsy schedule and remove Cycle 6 Day 7 and Follow-Up Tumor Assessment visit biopsies

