1. LIST OF ABBREVIATIONS

| Abbreviation | Meaning |
|--------------|---|
| AE | Adverse event |
| ATC | Anatomical Therapeutic Chemical |
| Bpm | Beats per minute |
| °C | Degrees Celsius |
| CR | Complete response |
| CRF | Case Report Form |
| CT | Computed tomography |
| CV | Coefficient of variation |
| CTC, CTCAE | Common Terminology Criteria for Adverse Events |
| DCR | Disease control rate |
| ECG | Electrocardiogram |
| ECOG | Eastern Cooperative Oncology Group |
| °F | Degrees Fahrenheit |
| HER2 | Human epidermal growth factor receptor 2 |
| irCR | Complete disappearance of all lesions (whether measurable or not, and no new lesions) confirmation by a repeat, consecutive assessment no less than 4 weeks from the date first documented |
| irDCR | Immune-related Disease Control Rate |
| irORR | Immune-related Overall Response Rate |
| irPD | Increase in tumor burden $\geq 25\%$ relative to nadir (minimum recorded tumor burden) confirmation by a repeat, consecutive assessment no less than 4 weeks from the date first documented |
| irPR | Decrease in tumor burden $\geq 50\%$ relative to baseline confirmed by a consecutive assessment at least 4 weeks after first documentation |
| irRC | Immune-Related Response Criteria |
| irSD | Not meeting criteria for irCR or irPR, in absence of irPD |
| MedDRA | Medical Dictionary for Regulatory Activities |
| mmHg | Millimeter(s) of mercury |
| N | Number of observations |
| n | Number of subjects |
| NCI | National Cancer Institute |
| ORR | Objective response rate |

| Abbreviation | Meaning |
|--------------|--|
| OS | Overall Survival |
| PD | Progressive Disease |
| PFS | Progression-Free Survival |
| PR | Partial response |
| RECIST | Response Evaluation Criteria in Solid Tumors |
| SAE | Serious adverse event |
| SAP | Statistical Analysis Plan |
| SAS | Statistical Analysis System |
| SD | Stable Disease |
| Std dev | Standard Deviation |
| SPD | Sum of perpendicular diameters |
| SRC | Safety review committee |
| TEAE | Treatment-emergent adverse event |
| Vp | Viral particles |
| WHO | World Health Organization |

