4. SECONDARY OBJECTIVES

- To estimate the progression rate at 12 weeks after the start of one cycle of Ad-RTS-hIL-12 immunotherapy
- To evaluate the overall response rate (ORR), defined as the rate of complete response (CR) plus the rate of partial response (PR) at 12 weeks following the start of Ad-RTS-hIL-12 immunotherapy
- To evaluate the disease control rate (DCR), defined as the proportion of subjects who have a CR, PR, or stable disease at 12 weeks following the start of one cycle of Ad-RTS-hIL-12 immunotherapy
- To evaluate the number of subjects whose baseline tumor status (stable disease or PR) improves to PR or better at 12 weeks following the start of Ad-RTS-hIL-12 immunotherapy
- To compare radiographic responses by irRC with conventional reporting by RECIST
- To explore the impact of treatment on tumor and blood immune biomarkers

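### SAP 10.3 adds diameters to form the irRC tumour burden but applies 50% and 25% cut-offs that fit a sum of products, so irPR is generally under-called and irPD can be wrong in either direction

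*SAP*

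**What the plan says.** SAP section 10.3 describes the irRC measure in these words: "based on the sum of the 2 largest perpendicular diameters (SPD) of all index lesions at baseline to provide the total tumor burden". Section 1 (List of Abbreviations) expands SPD as "Sum of perpendicular diameters". The word product does not appear in either place.

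At follow-up, section 10.3 adds together "the SPD of the index lesions and of new, measurable lesions", the latter from 5 x 5 mm upwards. irPR is a "decrease in tumor burden $\geq 50\%$ relative to baseline"; irPD is a rise of at least 25% from nadir. Both need confirmation at least 4 weeks later. irORR and irDCR are then analysed in the same way as the RECIST ORR and DCR.

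Section 4 gives a secondary objective that depends on this derivation: "To compare radiographic responses by irRC with conventional reporting by RECIST".

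For full detail, section 10 refers to the protocol: Section 9.2.2.7 for irRC and Appendix 16.3 for RECIST v1.1. The supplied protocol contains neither.

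**The concern.** A sum of diameters is a linear measure, whereas a sum of products behaves like an area. The same percentage cut-off means very different amounts of tumour change on the two scales. Both places in the SAP that define SPD give the linear form, so a programmer who follows the SAP will add diameters.

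At stake are irORR, irDCR and the comparison of irRC with RECIST. If the burden is on the wrong scale, part of any difference between the two criteria comes from the formula and not from how the tumours behaved.

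**Working it through.** The plan prints no figure that depends on this definition, so there is nothing to reproduce first. The check converts the cut-offs between scales and then works through lesion examples.

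**Inputs**
- irPR cut-off 50% and irPD cut-off 25%, with new lesions added to the burden: SAP 10.3.
- RECIST PR, a "decrease of at least 30% in the sum of diameters of target lesions", and RECIST PD, a 20% rise with at least 5 mm: protocol Appendix 4 (modified RECIST). The SAP prints neither figure. I assume that its RECIST v1.1 uses the same ones.

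**Uniform change in existing lesions.** If every diameter is multiplied by f, the sum of diameters is multiplied by f and the sum of products by f².

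| Category | Change in diameter needed, sum of diameters (as written) | Change in diameter needed, sum of products | RECIST (assumed) |
|---|---|---|---|
| PR | −50% (product: 1 − 0.5² = −75%) | 1 − √0.5 = −29.3% | −30% |
| PD | +25% (product: 1.25² − 1 = +56.25%) | √1.25 − 1 = +11.8% | +20% |

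Example, one 40 x 30 mm lesion (sum 70, product 1200):
- Shrinks 30% to 28 x 21: sum 49 (−30%, not irPR); product 588 (−51%, irPR); longest diameter −30%, RECIST PR.
- Grows 20% to 48 x 36: sum 84 (+20%, not irPD); product 1728 (+44%, irPD); longest diameter +20% and +8 mm, RECIST PD.

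For uniform change, the two formulas disagree on irPR for shrinkage from 29.3% up to 50%, and on irPD for growth from 11.8% up to 25%.

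**New lesions.** Here the irPD error reverses.
- Stable 30 x 30 mm plus a new 10 x 10 mm: sum 60 to 80 (+33%, irPD); product 900 to 1000 (+11%, not irPD).
- In general, with one stable D x D lesion and a new d x d lesion, the sum rises by d/D and the product by (d/D)². irPD is reached at d ≥ 0.25D on the sum and only at d ≥ 0.50D on the product.

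**Mixed index lesions.** irPR can also reverse. If a 40 x 40 mm lesion is stable while five 10 x 10 mm lesions vanish, the sum goes from 180 to 80 (−56%, irPR) and the product from 2100 to 1600 (−24%, not irPR).

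**Illustrative simulation.** All inputs are assumptions: 1 to 5 index lesions, median long axis 25 mm, new lesions of 5 to 20 mm, 30,000 subjects per setting, no confirmation step. With everyone assessable, irDCR is 100% minus irPD.

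| Mean new lesions per subject | irPR, sum vs product | irPD, sum vs product | irDCR, sum vs product |
|---|---|---|---|
| 0 | 2.1% vs 17.1% | 19.9% vs 31.9% | 80.1% vs 68.1% |
| 0.5 | 1.3% vs 14.3% | 30.3% vs 35.4% | 69.7% vs 64.6% |
| 1 | 0.9% vs 11.7% | 39.9% vs 38.7% | 60.1% vs 61.3% |
| 2 | 0.3% vs 7.8% | 56.1% vs 45.8% | 43.9% vs 54.2% |

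The direction is what matters here, not the exact rates. irPR is lower on the sum in every setting, while the irPD and irDCR differences change sign as new lesions become more common.

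**The case against.** **This may be a drafting slip, with the governing definition elsewhere.** The 5 x 5 mm notation suggests two-dimensional measurement, and the words *products of* may simply have been dropped. Protocol Section 9.2.2.7 may define the burden correctly. This stands as a limit on what can be said about the analysis as it would actually be run. It does not clear the SAP: a correct definition there would leave the SAP in conflict with the section it cites.

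**The evidence for products is indirect.** This is partly right. The supplied protocol describes a randomised multicentre study, while the SAP describes a single-arm, single-centre one. The protocol's Amendment 1 summary contains the phrase "the sum of the products of the two longest diameters (SLD) is used to calculate Total Tumor Burden", but that is superseded text in a log. I use it only as a sign of how the sponsor has understood total tumour burden, not as a contradiction of the SAP. The same log shows a deleted rule that set progression at a 25% rise in total burden.

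**Agreement with RECIST supports products for PR only.** Correct. For PD, 11.8% on products lies further from 20% than the 25% on the sum does. After the fix, uniform growth from 11.8% to below 20% would be irPD but not RECIST PD. The two criteria also differ under either formula because the RECIST table in SAP 10.1 counts any new lesion as PD, whereas irRC adds it to the burden. Correcting the formula therefore removes an artefact; it does not make the criteria agree.

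**A reader might infer that irPR and irPD are both under-called and irDCR is overstated.** The documents do not support this. It holds for growth of existing lesions, but SAP 10.3 adds new lesions to the burden, and small ones weigh more on a sum of diameters.

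**Conclusion.** The SPD definition is wrong as written and should be fixed. Under uniform change in existing lesions, irPR needs a 50% fall in diameter instead of 29.3%, and irPD a 25% rise instead of 11.8%. irPR is generally under-called and irORR generally understated, although mixed-lesion patterns can reverse this. irPD is under-called for growth of existing lesions and can be over-called when new lesions drive it, so the direction of the irDCR bias cannot be stated in advance. Part of any irRC-versus-RECIST difference would be produced by the formula.

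The reach is limited to irORR, irDCR and that one secondary comparison. The safety primary endpoint, the RECIST-based ORR and DCR, and the sample size do not depend on it.

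The conclusion rests on reading the SAP literally. The RECIST contrast also assumes that the 30% and 20% cut-offs in the supplied protocol's Appendix 4 match the SAP's RECIST v1.1.

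**What to change.** In SAP 10.3 and in the abbreviation list, define SPD as the sum of the products of the two largest perpendicular diameters. State that this applies to index lesions at baseline and to index plus new measurable lesions at follow-up. Keep the 50% and 25% cut-offs. Check the wording against the protocol section that the SAP cites for irRC (9.2.2.7), and bring the two into line if they differ.

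The cost is two wording edits and the derivation code. No new data are needed, because the present formula already uses both diameters. The change should be made before the irRC outputs are programmed.

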5.2. Overall Study Design

This is a single-arm, single-center Phase Ib/II study to examine the safety, tolerability, and preliminary efficacy of providing one cycle of Ad-RTS-hIL-12 immunotherapy following achievement of stable disease or PR on standard first-, second-, or third-line chemotherapy in breast cancer subjects. The subject population includes subjects with locally advanced or metastatic breast cancer of all subtypes. The safety of this therapy and the preliminary evidence of efficacy will guide further studies. Subjects are required to be in stable disease or PR after completion of a minimum of 12 weeks on standard chemotherapy. Subjects who have progressive disease (PD) or a CR after standard chemotherapy are not eligible for the study. Following entry into the trial, subjects will go on a treatment holiday from the standard chemotherapy and enter an immunotherapy phase of treatment.

Scans will be conducted 6 and 12 weeks after the start of Ad-RTS-hIL-12 immunotherapy for determination of tumor response. Radiographic PD at Week 6 must be confirmed at least 4 weeks later, either at Week 12 or earlier if clinically necessitated. In cases of slow tumor growth, the investigator may wait until confirmation of PD at 12 weeks to resume chemotherapy. In cases of unequivocal progression, the investigator may resume chemotherapy prior to 12 weeks and the subject will be considered as treatment failure at 12 weeks.

Upon completion of Week 12, subjects who are considered to have stable disease or better will enter long-term follow-up for up to an additional 36 weeks. In the long-term follow-up period, scans will be performed at 18, 24, 36, and 48 weeks until a radiographic response of PD is confirmed.

The assessment of response will be based on Response Evaluation Criteria in Solid Tumors (RECIST) v1.1 using tumor measurements from contrast-enhanced computed tomography (CT). Tumor response will also be assessed by Immune-Related Response Criteria (irRC) ([Wolchok et al, 2009](#)). Eligible subjects will also be asked to consent to allow ZIOPHARM to obtain scans and tumor measurements taken both a) prior to initiating the prestudy standard chemotherapy and b) after a minimum of 12 weeks of prestudy standard chemotherapy, and not more than 4 weeks prior to study enrollment, in order to confirm their stable disease or PR study entry status.

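### Progression first seen at week 12 has no scheduled confirming scan, so under SAP 10.3 read literally it becomes irSD and counts as disease control in irDCR

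*SAP*

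**What the plan says.** **irRC definitions (SAP 10.3; the irPD definition also stands in the abbreviation list, SAP 1).** irPD is a rise in tumor burden of at least 25% over nadir, with "confirmation by a repeat, consecutive assessment no less than 4 weeks from the date first documented". irCR and irPR carry a similar requirement. irSD is what is left: "irSD: not meeting criteria for irCR or irPR, in absence of irPD".

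**Analysis.** "irORR and irDCR by irRC will be analyzed the same way as described above for tumor response using RECIST v1.1". In SAP 10.2 the DCR numerator is CR, PR or stable disease at week 12. Subjects who cannot be assessed count as non-responders. SAP 10.1 and 10.2 state no confirmation requirement for the RECIST response at week 12.

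**Scan schedule (SAP 5.2).** "Scans will be conducted 6 and 12 weeks after the start of Ad-RTS-hIL-12 immunotherapy for determination of tumor response". The confirmation rule for this period concerns week 6 only: "Radiographic PD at Week 6 must be confirmed at least 4 weeks later, either at Week 12 or earlier if clinically necessitated". Afterwards, "Upon completion of Week 12, subjects who are considered to have stable disease or better will enter long-term follow-up", and in that period "scans will be performed at 18, 24, 36, and 48 weeks until a radiographic response of PD is confirmed". The SAP does not say whether RECIST or irRC decides who has stable disease or better.

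**Purpose.** SAP 4 and 5.1.2 list the comparison of irRC with RECIST among the secondary objectives and endpoints.

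**The concern.** The irRC definition of progression needs a second scan, and the schedule provides none for subjects judged progressed for the first time at week 12. Because irSD is a remainder class, failure to confirm does not leave such a subject unclassified. It moves the subject into a category that irDCR counts as success. The same week-12 scan can then be a failure under RECIST and a success under irRC, not because the criteria read the tumor differently but because no later scan was planned.

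At stake are the irDCR estimate, which can only be pushed upward by this route, and the planned comparison of the two sets of criteria, which would mix a real difference in criteria with an effect of the scan schedule.

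**Working it through.** **1. The plan's own figure.** SAP 5.4 gives a maximum of 40 subjects and a maximum exact 95% half-width of 0.16. The Clopper-Pearson interval is widest at 20/40: 0.338 to 0.662, half-width (0.662 − 0.338)/2 = 0.162. The figure reproduces. The SAP gives no figure for irDCR or for unconfirmed irPD.

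**2. Tracing the rules.**

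| First progression | Later scheduled scan | RECIST at week 12 | irRC, read literally | In DCR? | In irDCR? |
|---|---|---|---|---|---|
| Week 6, still present at week 12 | Week 12, 6 weeks later (at least 4) | PD | irPD, confirmed | No | No |
| Week 12, judged progressed and not in follow-up | None | PD | irSD: irPD unconfirmed, irCR and irPR not met | No | Yes |
| Week 12, irPD-level rise but RECIST SD, RECIST deciding follow-up | Week 18 | SD | Not stated whether week 18 may revise week 12 | Yes | Not stated |

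The second row is the problem; the first is handled correctly.

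The third row can occur because the thresholds differ. With equal growth in both diameters, +25% in the sum of products is √1.25 − 1 = +11.8% in diameter. A +20% rise in diameter is 1.2² − 1 = +44% in the sum of products. The 20% RECIST threshold is taken from Appendix 4 of the supplied protocol and is an assumption for this SAP.

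**3. Do other SAP rules catch the second row?**
- The non-assessable rule in SAP 10.2 does not fit its wording: a readable week-12 scan showing growth has been assessed.
- The treatment-failure rule in SAP 5.2 covers chemotherapy resumed before week 12, not progression found at week 12.

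**4. Effect per subject.** Each subject moved from irPD to irSD adds 1/40 = 2.5 percentage points. The number of such subjects, k, is not in the documents. Illustration with true control of 16/40:

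| k | irDCR reported | Exact 95% interval |
|---|---|---|
| 0 | 16/40 = 40.0% | 24.9% to 56.7% |
| 2 | 18/40 = 45.0% | 29.3% to 61.5% |
| 4 | 20/40 = 50.0% | 33.8% to 66.2% |
| 8 | 24/40 = 60.0% | 43.3% to 75.1% |

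**5. A ceiling for k.** Assume exponential time to progression with a proportion p progression-free at week 12. Then S(12) = p, S(6) = √p, and the share failing between the two scans is √p − p.

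| p | √p − p | Of 40 |
|---|---|---|
| 0.3 | 0.548 − 0.300 = 0.248 | 9.9 |
| 0.5 | 0.707 − 0.500 = 0.207 | 8.3 |
| 0.7 | 0.837 − 0.700 = 0.137 | 5.5 |

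This is a ceiling under those assumptions. It includes deaths, subjects without a week-12 scan and subjects who resumed chemotherapy early. It also includes RECIST progression from new lesions that leaves total burden below the 25% threshold, which is properly irSD.

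**The case against.** **The rule may stand elsewhere.** SAP 10 refers to protocol section 9.2.2.7 for irRC. The supplied protocol has no such section and describes a different, randomized two-arm design using mRECIST. The missing section might settle the matter. This limits certainty, but the SAP's own text in 10.3 gives the result traced above, and nothing supplied overrides it.

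**The default to irSD is inferred.** The SAP nowhere says that unconfirmed irPD becomes irSD. An analyst might use the non-assessable rule and reach the opposite answer. This stands as a caution. The literal definition still leads to irSD, and the possibility of two answers is itself a reason to write the rule down.

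**Some subjects may be scanned again.** A reader might infer that nobody with an irPD-level rise at week 12 ever has a confirming scan. The documents do not support that. If irRC decided entry to follow-up, a subject classed as irSD would be scanned at week 18. If RECIST decided it, subjects with an irPD-level rise who are RECIST SD would be. The gap is certain only for those judged progressed at week 12 and therefore not in follow-up.

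**irORR.** A reader might also infer that irORR is deflated by construction. That is not shown. A response first seen at week 6 can be confirmed at week 12. One first seen at week 12 belongs to a subject who enters follow-up and is scanned at week 18, and the SAP does not say that scan may not confirm it.

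**Confirmation is part of irRC.** A comparison with RECIST may properly include it. That is fair where a second scan was scheduled and did not confirm. It does not cover the case where none was scheduled.

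**Importance.** irRC is an additional assessment serving a secondary objective. This stands and limits the weight of the point.

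**Conclusion.** The point holds in a limited form. On the SAP's literal wording, an irPD-level increase first seen at week 12 with no later scan is irSD and enters the irDCR numerator, while a subject who is RECIST PD on that scan is not in the RECIST DCR. This biases irDCR upward and confounds the irRC-versus-RECIST comparison.

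The size is 2.5 percentage points per subject at n=40, and more per subject if fewer are treated, because 40 is a maximum. The 14% to 25% range (about 5 to 10 of 40) is an upper bound. It rests on an exponential shape and a 30% to 70% range that do not come from the documents, and should not be read as an expected count.

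Progression first seen at week 6 and confirmed at week 12 is classified correctly. RECIST ORR, RECIST DCR and the primary safety endpoint are unaffected. The SAP should be corrected on this point, but the trial's main conclusions do not depend on it.

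**What to change.** Amend SAP 10.3 as follows:

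1. Count an irPD-level increase first seen at week 12 with no later scan as not controlled in irDCR. Add a sensitivity analysis that classifies these subjects as irSD, and report how many there are.
2. State which criterion defines stable disease or better for this analysis, and whether the week-18 scan may confirm a week-12 irRC result.
3. Report irRC and RECIST week-12 status on the same unconfirmed basis in a paired per-subject cross-tabulation, beside the confirmed irRC result. Differences due to the criteria can then be told apart from differences due to confirmation.

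The cost is SAP wording and one extra table, with no extra scans. The reported irDCR may be lower than under the present wording.

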5.1.2. Secondary Endpoints

Secondary endpoints are as follows:

- The proportion failed by 12 weeks is denoted as the progression rate survival and is derived based on the sum of progression events, death events, and subjects who discontinue the trial due to an Adverse event (AE).
- The ORR, defined as the rate of CR plus the rate of PR at 12 weeks following the start of Ad-RTS-hIL-12 immunotherapy
- The DCR, defined as the proportion of subjects who have a CR, PR, or stable disease at 12 weeks following the start of one cycle of Ad-RTS-hIL-12 immunotherapy
- The number of subjects whose baseline tumor status (stable disease or PR) improves to PR or better at 12 weeks following the start of Ad-RTS-hIL-12 immunotherapy
- The radiographic responses by irRC with conventional reporting by RECIST
- Tumor and serum immune biomarkers

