5.4. Sample size

A maximum of 40 subjects will be treated. Because this patient population is heterogeneous, it is difficult to define a threshold for a clear null and alternative hypothesis. This sample size will allow us to estimate an overall progression rate at 12 weeks with a maximum 95% exact confidence interval half-width of 0.16. This is based on an exact binomial calculation and is an estimate. However, analysis of progression-free survival will be conducted using Kaplan-Meier methods.

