10. EFFICACY

The tumor response will be assessed by RECIST v1.1 and irRC. Full details concerning the use of RECIST v.1.1 may be found in the Appendix 16.3 in the protocol and for irRC can be referred to the Section 9.2.2.7 in the protocol.

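### The SAP sets out to compare irRC with RECIST in the same subjects but plans only separate rates, with no interval for the within-subject difference and no count of disagreements

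*SAP*

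**What the plan says.** The comparison appears twice in the SAP: as an objective in Section 4 ("To compare radiographic responses by irRC with conventional reporting by RECIST") and as an endpoint in Section 5.1.2 ("The radiographic responses by irRC with conventional reporting by RECIST"). Neither entry names a measure of difference or agreement.

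The two criteria are read in the same people. Section 5.2 opens with "This is a single-arm, single-center Phase Ib/II study", and Section 10 says "The tumor response will be assessed by RECIST v1.1 and irRC".

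The analysis is in Sections 10.1 to 10.3. ORR and DCR by RECIST v1.1 at 12 weeks are summarized by HER2 status and overall, each with an exact two-sided 95% interval. Subjects who cannot be assessed count as non-responders. For irRC, Section 10.3 adds that "irORR and irDCR by irRC will be analyzed the same way as described above for tumor response using RECIST v1.1". The SAP contains no cross-tabulation, discordance count, paired difference, agreement statistic or paired test.

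Section 5.4 sets the size: "A maximum of 40 subjects will be treated", "with a maximum 95% exact confidence interval half-width of 0.16" for the 12-week progression rate. It gives no hypothesis, because "it is difficult to define a threshold for a clear null and alternative hypothesis".

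**The concern.** When two criteria are applied to the same subjects, the information about how they differ lies in the subjects they classify differently. Two marginal rates reduce that to a net figure. The net figure has a sampling error that depends on the number of discordant subjects, and neither marginal interval contains that number.

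Two things are lost. First, a moderate difference between the criteria cannot be judged, because no interval for it is planned. Second, disagreements in opposite directions offset each other and leave no trace in the rates.

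Two-way disagreement is plausible from the definitions. Under the SAP 10.1 table a new lesion means PD, whereas under irRC measurable new lesions are added to the tumor burden and irPD needs a confirmed increase of at least 25%. That moves some subjects from PD to irSD. In the other direction, a 25% increase in a sum of products corresponds to uniform growth in diameter of about 12% (√1.25 = 1.118). If the RECIST appendix that the SAP cites uses the 20% diameter threshold given in Appendix 4 of the supplied protocol, growth between about 12% and 20% would be RECIST SD but could be irPD.

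At stake is one of six secondary objectives.

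**Working it through.** **Inputs.** From the SAP: n = 40 (maximum, Section 5.4), one arm (5.2), both criteria applied (10), exact 95% intervals for each rate (10.1 to 10.3). The documents give no discordance rates, so those below are assumptions.

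**1. The plan's own figure.** The Clopper-Pearson limits for x of n are the 0.025 quantile of Beta(x, n − x + 1) and the 0.975 quantile of Beta(x + 1, n − x). Over x = 0 to 40 the widest interval is at 20/40: 0.338 to 0.662, half-width (0.662 − 0.338)/2 = 0.162. The stated 0.16 is reproduced. It describes one proportion, not the difference between two criteria.

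**2. The planned output does not determine the comparison.** Take RECIST 20/40 (0.338 to 0.662) and irRC 28/40 (0.535 to 0.834). The difference is 8/40 = 20 points. Let b be subjects positive by irRC only and c those positive by RECIST only, so b − c = 8. Two of the tables with these margins are:

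- b = 8, c = 0 (both 20, neither 12). Exact McNemar p = 2 × 0.5^8 = 0.008.
- b = 20, c = 12 (both 8, neither 0). Two-sided binomial test of 20 out of 32 at 0.5: p = 0.215.

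The large-sample paired interval shows the same spread, with SE = √[b + c − (b − c)²/n]/n:

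- 8 against 0: √(8 − 64/40)/40 = √6.4/40 = 0.063, so 0.20 ± 1.96 × 0.063, about 8 to 32 points.
- 20 against 12: √(32 − 64/40)/40 = √30.4/40 = 0.138, so 0.20 ± 1.96 × 0.138, about −7 to 47 points.

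The four planned rates and their intervals would be identical in both cases.

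**3. Two-way disagreement.** With 4 against 4 discordant, the marginal rates are equal and the difference is 0, yet 8 of 40 subjects (20%) are classified differently. McNemar gives p = 1 and the paired difference is also 0. Only the cross-table shows this disagreement.

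**4. How much a paired analysis could show.** Assume a net shift of 20 points at n = 40, with RECIST disease control of 50%. Exact McNemar power is the total multinomial probability of all (b, c) with two-sided p < 0.05:

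- 20% against 0% discordant: 84%
- 25% against 5%: 57%
- 30% against 10%: 44%

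The 84% applies only if all reclassification runs one way. Power falls as two-way disagreement grows, and would also be lower with fewer than 40 subjects.

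**The case against.** The strongest reply is that the SAP is an estimation plan. It disclaims a null and alternative hypothesis, and showing rates side by side is a possible meaning of comparing the criteria. The two planned rates already give the point difference, since subjects who cannot be assessed stay in both denominators. Section 6.3 says listings will present all available data, so the pairs could be rebuilt. This stands as far as it goes. It is a reason to treat a McNemar p-value as optional, but not to leave out an interval for the difference. Rebuilding pairs from listings is not a prespecified analysis.

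Three stronger readings are tempting, and the documents do not support them.

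- A reader might infer that the plan cannot show a real difference. It can show a large one. At n = 40, whenever the two exact intervals fail to overlap, every possible paired table gives McNemar p < 0.05. For the RECIST counts tried (4, 8, 10, 16, 20 and 24), that takes a net 12 to 14 subjects, or 30 to 35 points.
- A reader might infer that separate intervals treat the criteria as two independent groups. They do not. A one-sample exact interval assumes nothing about the other rate.
- A reader might infer that overlapping intervals will be taken as agreement. The SAP states no such rule, so its plan should not be faulted by the performance of an overlap test.

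A further limit remains. SAP Section 10 cites protocol Section 9.2.2.7 and Appendix 16.3. The supplied protocol has neither and describes a randomized two-arm study using mRECIST. Whether the matching protocol specifies this comparison could not be checked.

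**Conclusion.** The point holds in a limited form. The SAP states a within-subject comparison and plans only marginal rates. It would report the direction and net size of any difference, but not its uncertainty and not how many subjects change category. The result in step 2, where the same rates go with p = 0.008 or p = 0.215, needs only n = 40 and those margins. The power figures (84%, 57%, 44%) rest on assumed discordance and illustrate the range; they are not predictions.

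The consequence is an incompletely answered secondary objective. The individual rates and their intervals, the primary safety analysis and the stated precision all stand.

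**What to change.** In SAP 10.3, make the following the analysis for the Section 4 objective:

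- A per-subject cross-table of RECIST v1.1 category by irRC category at week 12, overall and by HER2 status, with not evaluable kept as its own category and the discordant counts shown in each direction. This comes first, because it alone reveals offsetting disagreements.
- The paired differences irORR minus ORR and irDCR minus DCR, each with a paired 95% interval by a named method.
- If wanted, an exact McNemar p-value, labelled descriptive.

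Also state how confirmation is handled. Section 10.3 requires irCR, irPR and irPD to be confirmed at least 4 weeks later, while Sections 10.1 and 10.2 take RECIST status at 12 weeks and state no confirmation of response. Section 5.2 describes confirmation only for PD seen at week 6. Unless the two are aligned, the table would mix confirmation timing with differences between the criteria.

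The cost is SAP wording and one table from data already collected, with no new procedure and no change in n. The authors should also check whether the protocol that matches this SAP already specifies the comparison.
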